6.2 Glycemic control achievement rate (HbA1c)

(1) Patients to be tabulated and analyzed

Efficacy Analysis Set

(2) Details of tabulation and analysis

The glycemic control achievement rate for HbA1c (NGSP value) will be tabulated ($< 6.0\%$, $\geq 6.0\%$ / $< 7.0\%$, $\geq 7.0\%$) and a bar graph will be created at each testing time point (start of Nesina treatment, 1 month, 3 months, 6 months, and 12 months after Nesina treatment and last evaluation) (the unknown category will be excluded for the bar graph).

Total patients and patients who are taking concomitant insulin preparation, rapid-acting insulin secretagogues, SGLT-2 inhibitors, or other drugs will be tabulated.

(3) Number of tables and figures

Table 6.2-1 and Figures 6.2-1 and 6.2-2

6.3 Changes in Fasting blood glucose level, Fasting insulin level, Fasting Glucagon, HOMA-R, and HOMA- β

(1) Patients to be tabulated and analyzed

Efficacy Analysis Set

(2) Details of tabulation and analysis

For fasting blood glucose level, fasting insulin level, fasting glucagon, HOMA-R, and HOMA- β , summary statistics will be calculated at each testing time point (start of Nesina treatment, 1 month, 3 months, 6 months, and 12 months after Nesina treatment and last evaluation). For changes, summary statistics and the mean 95% confidence intervals will be

calculated and the paired t-test will be performed.

Measured values will be plotted and for the changes a bar graph will be created excluding the unknown category.

Total patients and patients who are taking concomitant insulin preparation, rapid-acting insulin secretagogues, SGLT-2 inhibitors, or other drugs will be tabulated.

(3) Number of tables and figures

Tables 6.3-1 and 6.3-5 and Figures 6.3-1 and 6.3-5

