1.0 Definition of Terms and Handling of Laboratory/Measured Data

1.1 Definitions

Term	Definition
Nesina	Nesina tablet(s) is abbreviated as Nesina in this statistical analysis plan.
SOC	System Organ Class of MedDRA/J MedDRA/J version 20.1 is used for this document.
HLGT	High level group term of MedDRA/J
PT	Preferred term of MedDRA/J
LLT	Lowest level term of MedDRA/J
Registered patients	Patients whose registration was approved
Survey sheet collected patients	Patients whose survey sheets were collected
Survey sheet uncollected patients	Of the registered patients, patients whose survey sheets were uncollected.
Safety Analysis Set	Of the survey sheet collected patients, patients who were evaluated for safety analysis. For tabulation, the description of “total” means the Safety Analysis Set.
Not Safety Analysis Set	Of the survey sheet collected patients, patients who were excluded from safety analysis
Efficacy Analysis Set	Of the Safety Analysis Set, patients who were evaluated for efficacy analysis
Not Efficacy Analysis Set	Of the Safety Analysis Set, patients who were excluded from the efficacy analysis
First date of Nesina treatment	Of the start dates of the Nesina treatment period in patients, the earliest date is defined as the first date of Nesina treatment.
Last date of Nesina treatment	Of the last dates of the Nesina treatment in patients, the latest date is defined as the last date of Nesina treatment. If Nesina treatment is continued and the year, month, and date of the continued treatment period are specified, the year, month, and date of the continued treatment period are defined as the last date of Nesina treatment. If the data for the year, month, and date of the continued treatment period are missing, the following date is defined as the last date of Nesina treatment. (1) First date of Nesina treatment + 1 year (same month and date) for continued treatment of Nesina. (2) Latest date at which the following examinations/observations will be performed for the not-continued treatment of Nesina: 
 • [Date of examinations/ observations] 
 • Compliance with Nesina treatment

Term	Definition
	
 • Compliance with diet/exercise therapy • Laboratory tests • Body weight • Waist circumference • Pulse rate • Blood pressure • Electrocardiography • Tests for coronary atherosclerosis and arteriosclerosis

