Mean daily dose of Nesina	
Calculate using the following formula: Total of “daily dose of Nesina \square Nesina treatment period at the relevant dose” / Nesina treatment period. For the calculation of Nesina treatment period, refer to the above.
 
If the daily dose of Nesina is a number outside specification in the survey sheet , handle the dose as follows:
 
 • < 6.25 mg \rightarrow 3.125 mg • > 25 mg \rightarrow 50 mg
HbA1c (NGSP value)	
The NGSP value only will be used in this analysis.
 
For the HbA1c (JDS value), calculate using the following formula: NGSP value (%) = $1.02 \times \text{JDS value (\%)} + 0.25\%$
 
The HbA1c (international standard value) will be handled as the NGSP value.

Change in HbA1c	For HbA1c converted to the NGSP value, calculate using the following formula: Laboratory value at each testing time point – Laboratory value at the start of Nesina treatment.
Glycemic control achievement rate	
Divide the following two categories for the glycemic control achievement rate: HbA1c (NGSP converted value) [Unit %] NGSP (%): < 6.0, \geq 6.0 / < 7.0, \geq 7.0

non-HDL cholesterol	Calculate using the following formula: “Total cholesterol” – “HDL cholesterol.”
HOMA-R	Calculate using the following formula: Fasting insulin level ($\mu\text{U/mL}$) \times Fasting blood glucose level (mg/dL) / 405. Indicate to one decimal place rounded from two decimals. For calculation, use the values of fasting insulin level and fasting blood glucose level measured at the same day.
HOMA- β	
Calculate using the following formula: Fasting insulin level ($\mu\text{U/mL}$) \times 360 / (Fasting blood glucose level [mg/dL] – 63). Indicate to one decimal place rounded from two decimals.
 
For calculation, use the fasting insulin level and fasting blood glucose level measured at the same day. Do not use the fasting blood glucose level of < 63 for calculation

Summary statistics	Number of patients, mean, standard deviation, minimum, first quartile, median, third quartile, and maximum.

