1.5 Handling of Laboratory/Measured Data

The evaluation time points for vital signs and laboratory tests will be at the start of Nesina treatment, 1 month, 3 months, 6 months, and 12 months after the start of Nesina treatment, and last evaluation.

The evaluation time points for electrocardiography, waist circumference, and coronary atherosclerosis and arteriosclerosis will be at the start of Nesina treatment, 12 months after the start of Nesina treatment, and last evaluation.

If multiple data exist within the relevant time point, calculate the absolute value of a difference in number of days from the reference number of days and select the minimum absolute value as the datum of the relevant evaluation time point. If the absolute values are same, select the datum at the latest examination/measurement day.

If "On treatment at 12 months after Nesina treatment" is selected in Section "Current Status of Nesina Treatment" in the survey sheet, all values will be used for analysis. If "On treatment at 12 months after Nesina treatment" is not selected, the values before the next day of the last administration of Nesina will be used for analysis.

The start day of Nesina treatment is defined as 0 days.

[Vital signs and laboratory test values]

Evaluation time point	Reference number of days	Lower limit of window	Upper limit of window
At start of Nesina treatment	0 days	30 days before Nesina treatment	Start day of Nesina treatment
1 month after start of Nesina treatment	30 days	1 day after start of Nesina treatment	60 days after start of Nesina treatment
3 months after start of Nesina treatment	90 days	61 days after start of Nesina treatment	136 days after start of Nesina treatment
6 months after start of Nesina treatment	180 days	137 days after start of Nesina treatment	273 days after start of Nesina treatment
12 months after start of Nesina treatment	360 days	274 days after start of Nesina treatment	456 days after start of Nesina treatment
At last evaluation	Select the latest datum from 1 to 456 days after the start of Nesina treatment		

[Electrocardiography and waist circumference]

Evaluation time point	Reference number of days	Lower limit of window	Upper limit of window
At start of Nesina treatment	0 days	30 days before Nesina treatment	Start day of Nesina treatment
12 months after start of Nesina treatment	360 days	1 day after start of Nesina treatment	456 days after start of Nesina treatment

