5.19.3 Electrocardiography

(1) Patients to be tabulated and analyzed

Safety Analysis Set

(2) Details of tabulation and analysis

For assessment of electrocardiogram, cross tabulation will be used for the categories described below.

Total patients and patients who are taking concomitant insulin preparation, rapid-acting insulin secretagogues, SGLT-2 inhibitors, or other drugs will be tabulated.

Parameter	Category
ECG results at start of Nesina treatment	Clinical abnormal findings (Yes or No) or Not performed
ECG results at 12 months after start of Nesina treatment	Clinical abnormal findings (Yes or No) or Not performed
ECG results at last evaluation	Clinical abnormal findings (Yes or No) or Not performed

(3) Number of tables and figures

Table 5.19.3

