6.4 Changes in HbA1c, etc. by Factor Probably Affecting Efficacy

(1) Patients to be tabulated and analyzed

Efficacy Analysis Set

(2) Details of tabulation and analysis

For changes in HbA1c (NGSP values), summary statistics and the mean 95% confidence intervals will be calculated and the paired t-test will be performed at each testing time point (start of Nesina treatment, 1 month, 3 months, 6 months, and 12 months after Nesina treatment and last evaluation).

The glycemic control achievement rate for HbA1c (< 6.0%, ≥ 6.0% / < 7.0%, ≥ 7.0%) at each testing time point (start of Nesina treatment, 1 month, 3 months, 6 months, and 12 months after Nesina treatment and last evaluation) will be tabulated for the following parameters:

- i Sex (Male, Female)
- ii Age (< 65 years, ≥ 65 years)
- iii Age (< 75 years, ≥ 75 years)
- iv Concurrent liver disorder (No, Yes)
- v Concurrent renal disorder (No, Yes)
- vi HbA1c (NGSP value) at the start of Nesina treatment (< 6.0%, 6.0% to < 7.0%, 7.0% to < 8.0%, ≥ 8.0%, or Unknown)
- vii Mean daily dose of Nesina (> 25 mg, 25 to > 12.5 mg, 12.5 to > 6.25 mg, or 6.25 mg)
- viii Concomitant diabetic drugs (α -glucosidase inhibitors, thiazolidines, sulfonylureas, biguanides, rapid-acting insulin secretagogues, or insulin preparations, DPP-4 inhibitors, GLP-1 receptor agonists, SGLT2 inhibitors, combination of diabetic drugs, or other diabetic drugs)

Total patients and patients who are taking concomitant insulin preparation, rapid-acting insulin secretagogues, SGLT-2 inhibitors, or other drugs will be tabulated.

(3) Number of tables and figures

Tables 6.4-1 to 6.4-16

Statistical Analysis Plan
Nesina Tablets Specified Drug-use Survey "Type 2
Diabetes Mellitus: Combination Therapy With
Hypoglycemic Drug (Insulin Preparation or Rapid-acting
Insulin Secretagogues, Etc)"

Takeda Pharmaceutical Company Limited.

PPD

Version 2, Created on February 6, 2018

Table of Contents

1.0	Definition of Terms and Handling of Laboratory/Measured Data	1
1.1	Definitions	1
1.2	Important Identified Risks, Potential Risks, and Missing Information	11
1.3	Display digit	12
1.4	Level of Significance and Confidence Coefficient.....	13
1.5	Handling of Laboratory/Measured Data.....	13
1.6	Display Data Digit.....	14
2.0	Disposition of Patients (Patient Diagram).....	16
3.0	Patient Demographics	17
4.0	Details of Treatment.....	20
4.1	Compliance.....	21
4.1.1	Status of compliance with Nesina.....	21
4.1.2	Status of Compliance with Diet Therapy.....	22

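### SAP 6.2 compares HbA1c target rates across time in different, overlapping sets of patients, with no same-patient start rate and no interval for the change

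*SAP*

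**What the plan says.** SAP 6.2 covers the second of the two HbA1c outcomes in Protocol 10.5.1. It plans that "The glycemic control achievement rate for HbA1c (NGSP value) will be tabulated" at the start, 1, 3, 6 and 12 months and last evaluation, against targets of 6.0% and 7.0%, for total patients and each treatment group. SAP 1.1 supplies the split: "Divide the following two categories for the glycemic control achievement rate". A bar graph follows, in which "the unknown category will be excluded for the bar graph". Section 6.2 contains no paired comparison, interval or test.

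Four other rules decide who is in each bar:

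- **Start value (SAP 1.5).** It must fall between 30 days before treatment and the start day. Section 6.4 vi carries an Unknown start-HbA1c category, so missing start values are expected.
- **Values after stopping (SAP 1.5).** For patients not on treatment at 12 months, "the values before the next day of the last administration of Nesina will be used for analysis".
- **Last evaluation (SAP 1.5).** The rule is "Select the latest datum from 1 to 456 days after the start of Nesina treatment".
- **Efficacy Analysis Set (SAP 1.1).** It is defined as "Of the Safety Analysis Set, patients who were evaluated for efficacy analysis". The exclusion table in SAP 2.0 does not require both a start and a later HbA1c.

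Other outcomes are treated differently. In 6.1 the change in HbA1c has a 95% CI and a paired t-test. In 5.19.3, "For assessment of electrocardiogram, cross tabulation will be used for the categories described below", with the start result as one of the categories.

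**The concern.** A reader of Figures 6.2-1 and 6.2-2 will compare the start bar with the 12-month bar and take the difference as the change in control. The two bars hold overlapping but different people. A patient who stops early, or has no value in the 12-month window, is in the start bar only. A patient with no start value can be in a later bar only. The visible change therefore mixes change within patients with change in who is counted.

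If poorly controlled patients more often lack a later value, the bar rises with no effect of treatment. If well-controlled patients do, it falls. Nothing in 6.2 lets the reader separate the two components, and no precision is attached to the change. Protocol 10.5.3 singles out the 12-month rate for the analysis of factors, so that bar will carry weight.

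**Working it through.** The documents give no start rate, missing-data rate or expected change for this outcome, so there is no stated figure to reproduce. All inputs below are assumptions chosen to show a range.

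**1. Fixed status, no drug effect.** Let p0 be the share below 7.0% at the start, and let dg and db be the shares lacking a 12-month value among patients below and not below 7.0%. If nobody's status changes, the 12-month bar reads

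p0(1 − dg) / [p0(1 − dg) + (1 − p0)(1 − db)].

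In counts, with 900 patients, p0 = 20%, dg = 10% and db = 30%: 180 start below 7.0% and 720 do not; 180 × 0.9 = 162 and 720 × 0.7 = 504 remain. The bar reads 162/666 = 24.3% against 180/900 = 20.0% at the start, a rise of 4.3 points.

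| p0 | dg / db | 12-month bar | Shift (points) |
|---|---|---|---|
| 20% | 20% / 20% | 20.0% | 0 |
| 20% | 10% / 20% | 22.0% | +2.0 |
| 20% | 10% / 30% | 24.3% | +4.3 |
| 20% | 10% / 40% | 27.3% | +7.3 |
| 10% | 10% / 30% | 12.5% | +2.5 |
| 40% | 10% / 30% | 46.2% | +6.2 |

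Over p0 from 10% to 40% and all the unequal patterns tried, up to 15%/45%, the shift ran from +1.1 to +10.7 points. Reversing the pattern (p0 = 20%, dg = 30%, db = 10%) gives 0.14/(0.14 + 0.72) = 16.3%, a fall of 3.7 points.

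**2. Same patients.** In the counted example the start rate among the 666 patients with both values is also 162/666 = 24.3%, so the paired difference is 0.

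**3. Last evaluation.** If a share f of those lacking a 12-month value has some post-start value, replace d by d(1 − f). For p0 = 20% and 10%/30%, the bar reads 21.8% at f = 50%, 20.3% at f = 90% and 20.0% at f = 100%.

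**4. Table against figure.** SAP 6.2 excludes Unknown only from the bar graph. If Table 6.2-1 keeps Unknown in its denominator, the same example gives 162/900 = 18.0%, a fall of 2.0 points beside a bar that rises by 4.3.

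**5. Within-patient variation.** Assume start HbA1c with mean 8.0% and SD 1.2, correlation 0.7 with the 12-month value, no drug effect, 900 patients, and log-odds of a missing 12-month value rising by 0.4 to 0.8 per SD of start HbA1c. The unpaired rate rises by 1.1 to 1.9 points with 15% missing, 1.8 to 3.2 with 25% and 3.0 to 5.3 with 40%. In the same patients the difference is −0.4 to −2.1 points, which is regression to the mean. At 25% missing with the steeper slope, the 95% half-width is 3.4 points for the paired difference, against 4.1 if the two rates are treated as independent.

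**6. What pairing leaves.** A second simulation assumed true mean 7.8, SD 1.0, within-patient SD 0.4, and missingness of 10% below 7.0% and 30% otherwise. If missingness follows the start value, the unpaired shift is +3.0 and the paired difference −1.7 points. If it follows the current value, they are +4.7 and +1.7.

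**The case against.** A reader might infer that the SAP never pairs this outcome. The documents do not support that. For start HbA1c (item vi), SAP 6.4 tabulates "The glycemic control achievement rate for HbA1c" at every time point within categories cut at 6.0, 7.0 and 8.0. Adding the two categories below 7.0% and the two above gives the start-by-later table for the 7.0% target; the lowest category against the rest gives it for 6.0%. With counts printed, the same-patient start rate follows. In step 1 these strata would stay at 100% and 0%, which would expose the artefact.

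A reader might also infer that control will appear to improve because poorly controlled patients leave. No document gives a dropout rate or says who is missing. With equal missingness the shift is zero, and the rise concerns rates among patients with a known value.

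Three further points stand. The last-evaluation rate keeps early discontinuers who have any post-start value. The 12-month window opens at day 274, so a patient who stops after that can still contribute. And this is a single-arm survey, not sized on statistical grounds, whose protocol asks only for tabulation, while 6.1 already tests mean HbA1c within patients.

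These points narrow the concern without closing it. Section 6.4 vi gives neither a net change nor an interval, and its strata move by chance variation alone: under the assumptions of step 5, about 22% of the 7.0 to < 8.0% stratum and 4% of the ≥ 8.0% stratum fall below 7.0% at 12 months with no drug effect. At last evaluation, patients with no post-start value still count only at the start, and those with no start value only later. The paired t-test concerns the mean, not the share at target.

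**Conclusion.** The point holds as a limited, inexpensive improvement to 6.2. Two things follow from the text alone: the bars at different time points need not contain the same patients, and the change in the rate has no same-patient reference and no interval.

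The size is conditional. With missingness related to HbA1c, shifts of a few points without drug effect are plausible (about 1 to 5 in the model with within-patient variation, up to 10.7 in the most unequal fixed-status case). With unrelated missingness there is none, and the direction depends on who is missing. Pairing removes only the change in who is counted. It does not remove regression to the mean or selection on current HbA1c, which left −1.7 to +1.7 points in step 6.

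**What to change.** In SAP 6.2 only, for total patients and each treatment group, for each later time point including last evaluation, and for each threshold, add:

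1. the number of patients with both a start and a later value;
2. the start rate in those patients beside their later rate;
3. the 2x2 table of start by later status;
4. the paired difference with its two-sided 95% CI (a McNemar test is optional).

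Draw Figures 6.2-1 and 6.2-2 with the same-patient start rate next to each later rate, and show n and the Unknown count at each point. State the denominator of Table 6.2-1. Add a sentence saying that pairing removes only the change in who is counted, not regression to the mean or selection on current HbA1c.

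Do not extend McNemar tests to 6.4. Within a start-HbA1c stratum everyone begins on the same side of each target, and the Unknown stratum has no start status. The eight factors have 30 levels, so five later time points and two thresholds would give 30 × 5 × 2 = 300 tests for total patients alone.

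The cost is a few lines of SAP text and some table columns from data already held. No new data are needed.

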6.4 Changes in HbA1c, etc. by Factor Probably Affecting Efficacy

(1) Patients to be tabulated and analyzed

Efficacy Analysis Set

(2) Details of tabulation and analysis

For changes in HbA1c (NGSP values), summary statistics and the mean 95% confidence intervals will be calculated and the paired t-test will be performed at each testing time point (start of Nesina treatment, 1 month, 3 months, 6 months, and 12 months after Nesina treatment and last evaluation).

The glycemic control achievement rate for HbA1c (< 6.0%, ≥ 6.0% / < 7.0%, ≥ 7.0%) at each testing time point (start of Nesina treatment, 1 month, 3 months, 6 months, and 12 months after Nesina treatment and last evaluation) will be tabulated for the following parameters:

- i Sex (Male, Female)
- ii Age (< 65 years, ≥ 65 years)
- iii Age (< 75 years, ≥ 75 years)
- iv Concurrent liver disorder (No, Yes)
- v Concurrent renal disorder (No, Yes)
- vi HbA1c (NGSP value) at the start of Nesina treatment (< 6.0%, 6.0% to < 7.0%, 7.0% to < 8.0%, ≥ 8.0%, or Unknown)
- vii Mean daily dose of Nesina (> 25 mg, 25 to > 12.5 mg, 12.5 to > 6.25 mg, or 6.25 mg)
- viii Concomitant diabetic drugs (α -glucosidase inhibitors, thiazolidines, sulfonylureas, biguanides, rapid-acting insulin secretagogues, or insulin preparations, DPP-4 inhibitors, GLP-1 receptor agonists, SGLT2 inhibitors, combination of diabetic drugs, or other diabetic drugs)

Total patients and patients who are taking concomitant insulin preparation, rapid-acting insulin secretagogues, SGLT-2 inhibitors, or other drugs will be tabulated.

(3) Number of tables and figures

Tables 6.4-1 to 6.4-16

Statistical Analysis Plan
Nesina Tablets Specified Drug-use Survey "Type 2
Diabetes Mellitus: Combination Therapy With
Hypoglycemic Drug (Insulin Preparation or Rapid-acting
Insulin Secretagogues, Etc)"

Takeda Pharmaceutical Company Limited.

PPD

Version 2, Created on February 6, 2018

Table of Contents

1.0	Definition of Terms and Handling of Laboratory/Measured Data	1
1.1	Definitions	1
1.2	Important Identified Risks, Potential Risks, and Missing Information	11
1.3	Display digit	12
1.4	Level of Significance and Confidence Coefficient.....	13
1.5	Handling of Laboratory/Measured Data.....	13
1.6	Display Data Digit.....	14
2.0	Disposition of Patients (Patient Diagram).....	16
3.0	Patient Demographics	17
4.0	Details of Treatment.....	20
4.1	Compliance.....	21
4.1.1	Status of compliance with Nesina.....	21
4.1.2	Status of Compliance with Diet Therapy.....	22

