##### 4.1 Inclusion Criteria

Patients who meet the following criterion are included in this survey:

Patients who have had an inadequate response to the following medications/therapies:

- Use of one hypoglycemic agent such as insulin preparations and rapid-acting insulin secretagogues, excluding other types of hypoglycemic agents (e.g.,  $\alpha$ -glucosidase inhibitors, thiazolidines, sulfonylureas, biguanides)\*, in addition to dietary/exercise therapy

\*For use of Nesina Tablets in combination with these agents, a specified drug-use survey is currently ongoing.

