##### 10.5.3 Factors Probably Affecting Efficacy

For the changes in HbA1c and glycemetic control achievement rate at 12 months after the start of treatment, the following will be stratified: patient demographics (e.g., sex, age, HbA1c at the start of Nesina treatment) and details of treatment (e.g., status of Nesina treatment, status of concomitant medications).

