1.4 Level of Significance and Confidence Coefficient

Two-sided 5%, two-sided 95%.

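### SAP 6.4 tests HbA1c change against zero within each level but never compares levels, and grouping by baseline HbA1c distorts the gradient through regression to the mean

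*SAP*

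**What the plan says.** Item numbers here follow the current SAP, whose section 6.4 lists eight factors. For HbA1c change by factor it asks for summary statistics and 95% CIs of the mean, and states that "the paired t-test will be performed at each testing time point". Achievement rates are tabulated by the same factors. No difference between levels, interaction or model appears anywhere in SAP section 6. SAP 1.4 sets a two-sided 5% level.

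Item vi groups patients by "HbA1c (NGSP value) at the start of Nesina treatment", cut at 6.0, 7.0 and 8.0%. SAP 1.1 defines the change as "Laboratory value at each testing time point – Laboratory value at the start of Nesina treatment". The baseline is one reading from day −30 to day 0, because SAP 1.5 says to "select the minimum absolute value as the datum of the relevant evaluation time point".

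Protocol 10.5.3 asks for less: "For the changes in HbA1c and glycemetic control achievement rate at 12 months after the start of treatment, the following will be stratified". It names no test. By contrast, SAP 5.4.1 does compare levels for adverse drug reactions, using Fisher's exact and Mann-Whitney U tests.

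**The concern.** A factor affects efficacy if its levels differ. A paired t-test inside one level asks only whether that level's mean change differs from zero. Two levels with the same true change can land on opposite sides of 5% because one is smaller, and two levels with clearly different changes can both be significant without the difference being estimated.

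Item vi has a further problem. When patients are grouped on a single noisy reading and that reading is then subtracted, strata below the overall mean tend to rise and strata above it tend to fall, relative to the overall change, whether or not the drug works. The survey has no control group and the SAP carries no caveat. At stake are statements that the drug works in one subgroup but not another, or works better at high baseline HbA1c, which these tables could not support.

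**Working it through.** **The plan's own figures.** Eight factors × 2 outcomes (change and achievement rate) = 16, which matches Tables 6.4-1 to 6.4-16, so change is broken down by every factor. The planned 1,000 (Protocol 3.1) cannot be derived, since Protocol 3.2 says it has no statistical basis.

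**Part 1: equal true change, unequal levels.**

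Inputs:
- N = 800 in the efficacy set and SD of change 1.0, both assumed.
- Smaller level 15.1% of 800 = 121, leaving 679. The 15.1% is renal impairment in the earlier survey (Protocol 3.2), used as a proxy for concurrent renal disorder, which SAP 1.1 defines by a different coding query.

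Power comes from the noncentral t distribution with noncentrality δ√n / SD. For δ = 0.2:
- n = 121: 0.2 × 11 = 2.2, power 59%.
- n = 679: 0.2 × 26.06 = 5.21, power above 99.9%.
- Significant in the larger level only: 0.999 × (1 − 0.588) = 41%.

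| True change in both levels | Power, n = 121 | Significant in larger level only |
|---|---|---|
| −0.15 | 37% | 61% |
| −0.2 | 59% | 41% |
| −0.3 | 91% | 9.5% |
| −0.4 | 99.2% | 0.8% |

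At the planned 1,000 (151 vs 849), the figure at −0.2 is about 32%. A direct test of the difference errs in about 5% of surveys (simulated, 133 vs 867: 5.1 to 5.4%).

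The reverse failure also occurs. With true changes of 0.5 and 0.8 in levels of 133 and 867, both paired tests are significant with probability above 0.999, and the 0.3 difference is never estimated.

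**Part 2: regression to the mean in item vi, zero true change.**

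The documents give no HbA1c mean, SD or baseline-to-follow-up correlation (ρ). Assumed ranges: mean 7.5 to 8.0, SD 1.0 to 1.3, ρ 0.5 to 0.9, bivariate normal.

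Expected change in a stratum = −(1 − ρ) × (stratum baseline mean − overall mean).

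Example with mean 8.0, SD 1.0, ρ = 0.7:
- ≥ 8.0%: baseline mean 8.0 + 0.399/0.5 = 8.80; change −0.3 × 0.80 = −0.24.
- < 6.0%: baseline mean 8.0 − 0.0540/0.0228 = 5.63; change +0.3 × 2.37 = +0.71.
- Within the ≥ 8.0% stratum, the variance of change is 0.3² × 0.363 + (1 − 0.49) = 0.543, SD 0.74. With 400 patients (N = 800), 0.24/(0.74/20) = 6.5 standard errors, so rejection is practically certain. With 50 patients (N = 100), 0.24/(0.74/7.07) = 2.3 and rejection is about 62%.

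Over the whole range, for the ≥ 8.0% stratum:
- Expected fall: 0.08 to 0.69 points.
- Rejection at N = 800: about 95 to 100% of simulated runs.
- Rejection at N = 100, relevant because 6.4 is also tabulated by treatment group: about 25 to 90%.

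A stratum centred on the overall mean shows no artefact (7.0 to < 8.0% if the mean is 7.5).

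**Adding a uniform fall of 0.5.** With mean 8.0, SD 1.0 and ρ = 0.8, the < 6.0% stratum moves from +0.47 to −0.03 and the ≥ 8.0% stratum from −0.16 to −0.66. The gap is 0.63 in both cases: the rise disappears, but the false gradient does not.

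**Would a between-level test repair item vi?** No. With zero true change, ANOVA across the four baseline strata is significant in 100% of runs at N = 1,000 and in 84 to 100% at N = 300 (ρ 0.5 to 0.9).

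**The case against.** This is an uncontrolled descriptive survey. The protocol only asks for stratified tabulation, the wish to identify factors is read from a section heading, and no decision hangs on the p-values. Readers also see each level's mean, 95% CI and achievement rate, and can compare levels by eye. That much is fair, and it limits the harm. It does not justify the test: the SAP added p-values the protocol did not ask for, they address the wrong contrast for the heading above them, and separate intervals give neither the difference nor its uncertainty.

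Some stronger readings do not stand:
- A reader might infer that the p-values mostly reflect stratum size, or that discordant results are generally common. That depends on a modest true change. At −0.4 the pattern is under 1%, and the documents state no expected effect.
- A reader might infer that low-baseline strata must show significant rises. Entry requires an inadequate response to earlier therapy, so an overall fall is plausible. With a uniform −0.5 and ρ = 0.8, the < 6.0% stratum averages about −0.11 to +0.01. At ρ = 0.5 a rise persists.
- A reader might infer that every factor should be modelled. Mean daily dose (item vii) is averaged over the treatment period, so it is determined after baseline, and the drug classes in item viii are marked as overlapping in SAP 5.4.1. Neither suits a simple between-level contrast.

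**Conclusion.** The point holds. As written, SAP 6.4 tests the wrong contrast for its stated subject, and item vi builds in an artefact that its p-values will tend to endorse. The absence of any between-level comparison is plain from the text and needs no assumption. The direction of the item vi distortion, relative to the overall change, needs only a baseline-to-follow-up correlation below 1.

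The sizes are conditional. Discordance of 61% down to under 1% rests on an SD of change of 1.0, a 121/679 split borrowed from another survey's renal-impairment share, and true changes of −0.15 to −0.4. The 0.1 to 0.7 point fall in the ≥ 8.0% stratum rests on the assumed mean, SD and correlation ranges with zero true change. For a descriptive survey this is a moderate matter, worth correcting because the correction is cheap.

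**What to change.** In SAP 6.4:
- Keep the means and 95% CIs of change by level, and drop the within-level paired t-test p-values.
- For items i to v (sex, the two age splits, liver disorder, renal disorder), report the between-level difference in change at 12 months and at last evaluation with its 95% CI, adjusted for continuous baseline HbA1c and labelled exploratory.
- Keep item vi descriptive, without p-values, and state that regression to the mean is expected.
- Keep items vii and viii descriptive, without model-based contrasts.

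The cost is SAP wording, a few simple models and a line explaining the adjusted estimates. No new data are needed. The precision is usable: for 121 versus 679 with an SD of 1.0, the half-width of the unadjusted 95% CI is 1.96 × √(1/121 + 1/679) ≈ 0.19 HbA1c points.
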